10.5. Statistical Methods

Primary endpoint: Progression-free survival (PFS) as the number of months from baseline to death or progression, defined in Appendix 4. The duration of PFS will be summarized descriptively using Kaplan-Meier survival plots and life tables. The number and proportion with PFS of 6 months or more will be reported, adjusting for censoring using the life-table approach. If the number with PFS at least six months is 15 or more out of 25 evaluable patients, this will constitute evidence supporting an improvement over historic PFS rates.

Secondary endpoints: RECIST response will be calculated as in Appendix 4, and will be summarized by the number and percentage of patients, accompanied by 2-sided exact 95% confidence intervals. Overall survival will be summarized descriptively by Kaplan-Meier curves and life table estimates, as for PFS. Number and type of adverse events will be summarized descriptively by system organ class affected and by grade of event, overall and by dose. Vital signs and laboratory test results will be summarized descriptively (mean, SD, range) overall and by dose.

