2. STUDY OBJECTIVE

2.1. Primary Objective

To assess in a preliminary fashion the feasibility and efficacy of ibrutinib in combination with nivolumab in patients with previously-treated metastatic renal cell cancer (mRCC).

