10. STATISTICAL METHODS AND ANALYSIS

10.1. Subject Information

All patients receiving at least one cycle of therapy and are evaluable for response will be assessable for the primary endpoint of progression free survival (evaluable population).

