10.3. Sample Size Determination

In the RECORD-1 trial, PFS at 6 months was approximately 40%. Assuming that the ibrutinib plus nivolumab combination will increase the PFS rate from 40 to 70% at the 6 month timepoint, a sample size of 25 patients will provide 90% power and one-sided level 0.034 to detect this difference, with a critical value of 15 or more patients out of 25 experiencing PFS at 6 months. To account for dropouts, a total of 30 patients will be accrued. Efficacy analysis will be performed on all patients enrolled in the study regardless of dose level assignment; i.e., patients from each of the completed dose levels will be pooled as described in the study schema.

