10.4.2. Efficacy populations

Evaluable population:

The evaluable population will be the basis for the primary analysis of efficacy (progression-free survival). This population will include all patients who complete at least one cycle of therapy at either of the two planned dose levels and are evaluable for the primary response (progression-

free survival). Secondary analyses may require instead that patients be evaluable for secondary efficacy analyses (RECIST response, overall survival.)

Per-protocol population:

A supportive analysis may be carried out using the per-protocol population, defined as a subset of the evaluable population that further excludes patients who experienced deviations from protocol that may affect primary or secondary outcomes.

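### The success rule of 15 out of 25 is defined only at exactly 25 evaluable patients, although 30 are accrued and the number evaluable is not fixed

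*Combined protocol and SAP*

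**What the plan says.** Section 10.3 tests a 6-month PFS rate of 40% against 70% with 25 patients, one-sided level 0.034 and 90% power, "with a critical value of 15 or more patients out of 25 experiencing PFS at 6 months". It then adds: "To account for dropouts, a total of 30 patients will be accrued". No dropout rate is given. The same section says that "patients from each of the completed dose levels will be pooled as described in the study schema".

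Section 10.5 repeats the threshold for the analysis: "If the number with PFS at least six months is 15 or more out of 25 evaluable patients", this is evidence of improvement. It also says that the number and proportion with PFS of 6 months or more will be reported, "adjusting for censoring using the life-table approach".

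Two sections say who is evaluable:
- Section 10.1: "All patients receiving at least one cycle of therapy and are evaluable for response will be assessable for the primary endpoint".
- Section 10.4.2: "patients who complete at least one cycle of therapy at either of the two planned dose levels and are evaluable for the primary response". This set is the basis of the primary analysis, and its size is not capped.

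Section 2.1 sets the aim: "To assess in a preliminary fashion the feasibility and efficacy of ibrutinib in combination with nivolumab".

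**The concern.** A binomial cut-off has a given level and power only at one sample size. The plan accrues 30 so that about 25 remain, but the number that remains is random. If it is not 25, three readings are open:
- keep the count of 15;
- keep the proportion, 15/25 = 60%;
- test some 25 of the evaluable patients, without saying which.

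The plan does not choose. In an open-label single-arm trial, the choice would then be made with the outcomes in view.

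The denominator is also loose. A patient who progresses or dies in cycle 1 may have received a cycle (Section 10.1) without completing it (Section 10.4.2). A patient censored before 6 months contributes to a life-table estimate but has no defined place in a raw count.

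**Working it through.** **Inputs.** Section 10.3: null rate 0.40, alternative 0.70, n = 25, cut-off 15, accrual 30. The range n = 20 to 30 is an assumption, because no dropout rate is stated.

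**Formula.** With X the number of successes among n patients, level = P(X ≥ r | n, 0.40) and power = P(X ≥ r | n, 0.70), exact binomial.

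**The plan's own figure.** n = 25, r = 15: level 0.0344, power 0.9022. Both stated figures reproduce. The neighbouring cut-offs do not fit: 14 gives 0.0778 and 0.956, and 16 gives 0.0132 and 0.811.

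**The rule at other n.** The 60% cut-off is 0.6n rounded up.

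| n | Count of 15: level / power | 60% cut-off | 60%: level / power |
|---|---|---|---|
| 20 | 0.002 / 0.416 | 12 | 0.057 / 0.887 |
| 21 | 0.004 / 0.551 | 13 | 0.035 / 0.852 |
| 22 | 0.007 / 0.671 | 14 | 0.022 / 0.814 |
| 23 | 0.013 / 0.771 | 14 | 0.035 / 0.880 |
| 24 | 0.022 / 0.847 | 15 | 0.022 / 0.847 |
| 25 | 0.034 / 0.902 | 15 | 0.034 / 0.902 |
| 26 | 0.052 / 0.940 | 16 | 0.022 / 0.875 |
| 27 | 0.074 / 0.964 | 17 | 0.013 / 0.843 |
| 28 | 0.103 / 0.979 | 17 | 0.022 / 0.897 |
| 29 | 0.136 / 0.988 | 18 | 0.013 / 0.871 |
| 30 | 0.175 / 0.994 | 18 | 0.021 / 0.916 |

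**Conflicting verdicts.** 15/26 = 57.7% (exact one-sided p = 0.052) succeeds as a count and fails as 60%. 16/27 = 59.3% (p = 0.034) meets the planned level yet fails as 60%. For n = 26 to 30, the two readings disagree with probability P(15 ≤ X < 60% cut-off):
- true rate 40%: 0.030, 0.061, 0.081, 0.123, 0.154;
- true rate 70%: 0.065, 0.121, 0.082, 0.118, 0.078.

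**How likely n = 25 is.** Assume independent dropout at 5/30, the rate implied by going from 30 to 25. Then n is Binomial(30, 25/30), with P(n = 25) = 0.19, P(n > 25) = 0.42 and P(n < 25) = 0.38. At 10% dropout P(n > 25) = 0.82; at 20% it is 0.26. No common rate makes n = 25 more likely than 0.19.

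**Effect of the evaluable definition.** Suppose a fraction e of patients fail in cycle 1 and are left out. The null rate among the rest becomes 0.40/(1 − e). These values of e are assumed:
- e = 5%: 0.40/0.95 = 0.421, and P(X ≥ 15 | 25, 0.421) = 0.055;
- e = 10%: 0.40/0.90 = 0.444, and P(X ≥ 15 | 25, 0.444) = 0.087.

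**The case against.** Both sections print the count with its denominator, so keeping 15 while n grows to 30 drops half the rule. On the more natural 60% reading, the level at n = 26 to 30 is 0.013 to 0.022, below plan, and the loss is at most about 6 points of power (0.902 − 0.843). Testing exactly 25 evaluable patients is also a fair reading, since the other five are there only to cover dropouts. Efficacy is preliminary, PFS is mainly described by Kaplan-Meier and life-table methods, and any reader given x and n can compute the p-value.

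Much of this stands, and it limits the point. What remains is that the plan does not say which reading applies, the 60% reading has level 0.057 at n = 20, and the third reading does not say which 25 patients are tested and gives nothing when fewer than 25 are evaluable.

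Three stronger inferences are not supported:
- *The design arithmetic is wrong.* It is right at n = 25.
- *The trial runs at a one-sided level of 0.175.* That needs both the count reading and all 30 evaluable. The sentence in Section 10.3 about analysing everyone enrolled might suggest n = 30, but it is explained there as pooling across dose levels, and Section 10.4.2 names the evaluable set as primary.
- *The level is already 0.055 or 0.087 because early failures are excluded.* The documents give no early-failure rate, and Section 10.1 can be read as keeping these patients.

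**Conclusion.** The point holds as an under-specified decision rule, not as an arithmetic error. The plan's only efficacy threshold is defined at one value of n that is unlikely to be met exactly. Away from it, each usable reading departs from the stated level or power: the count inflates the level above 25 and loses power below it, while 60% keeps the level above 25 but loses some power at 26 to 29.

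The figures assume rates of 40% and 70%, independent patients, and a known 6-month status for everyone counted. The chance that n differs from 25 rests on an assumed dropout rate. It should be fixed, but the consequence is modest: the aim is preliminary and no action is tied to crossing the threshold.

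**What to change.** **1. Cut-offs.** In Section 10.5, replace the single cut-off with one for each number evaluable: the smallest whose exact one-sided level against 40% is at most about 0.035 (to three decimals). Report the exact one-sided p-value with it, and apply the same rule below 20.

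| Evaluable | Successes needed | Level | Power |
|---|---|---|---|
| 20 | 13 | 0.021 | 0.772 |
| 21 | 13 | 0.035 | 0.852 |
| 22 | 14 | 0.022 | 0.814 |
| 23 | 14 | 0.035 | 0.880 |
| 24 | 15 | 0.022 | 0.847 |
| 25 | 15 | 0.034 | 0.902 |
| 26 | 16 | 0.022 | 0.875 |
| 27 | 16 | 0.034 | 0.920 |
| 28 | 17 | 0.022 | 0.897 |
| 29 | 17 | 0.033 | 0.935 |
| 30 | 18 | 0.021 | 0.916 |

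Within this range it differs from 60% only at 20, 27 and 29. The ceiling is a choice, since the plan gives 0.034 only as the level at 25. A strict 0.0344 would change only n = 21 and 23, to 14 and 15 successes, with power 0.723 and 0.771; that gives up 13 and 11 points of power to avoid excesses under 0.001.

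**2. One evaluable definition.** State it in Section 10.4.2 and have Section 10.1 refer to it. Keep patients who progress or die in cycle 1 and count them as not successful, because the levels above assume a 40% null rate in the analysed set. Reword the sentence in Section 10.3 to say only that dose levels are pooled within that set.

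**3. Censoring before 6 months.** State whether such a patient is in the count, and how. The choice is the sponsor's. With 30 evaluable and 18 needed, counting one, two or three such patients as not successful gives power 0.871, 0.809 or 0.728. Excluding them and using the row for 29, 28 or 27 gives 0.935, 0.897 or 0.920, but the level then holds only if censoring is unrelated to outcome.

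**Cost.** One table and a few sentences, with no extra patients. Power is below 90% at 26, at 28 (marginally) and at every number below 25.

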10.4. Analysis Populations

10.4.1. Safety Population

The safety population will include all patients who receive at least one dose of either study drug. A baseline measurement and at least one laboratory, vital sign, or other safety-related measurement obtained after at least one dose of study medication may be required for inclusion in analyses of a specific safety parameter.

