11.1. Definitions

11.1.1. Adverse Events

An AE is any untoward medical occurrence in a subject administered a pharmaceutical product and which does not necessarily have a causal relationship with this treatment. An AE can therefore be any unfavorable and unintended sign (including a clinically significant abnormal laboratory finding, for example), symptom, or disease temporally associated with the use of an investigational study drug, whether or not considered related to the study drug ([ICH-E2A, 1995](#)).

For the purposes of this clinical study, AEs include events which are either new or represent detectable exacerbations of pre-existing conditions.

The term “disease progression” should not be reported as an adverse event term. As an example, “worsening of underlying disease” or the clinical diagnosis that is associated with disease progression should be reported.

Adverse events may include, but are not limited to:

- Subjective or objective symptoms provided by the subject and/or observed by the Investigator or study staff including laboratory abnormalities.
- Any AEs experienced by the subject through the completion of final study procedures.
- AEs not previously observed in the subject that emerge during the protocol-specified AE reporting period, including signs or symptoms associated with the underlying disease that were not present before the AE reporting period
- Complications that occur as a result of protocol-mandated interventions (eg, invasive procedures such as biopsies).

The following are NOT considered AEs:

- **Pre-existing condition:** A pre-existing condition is not considered an AE unless the severity, frequency, or character of the event worsens during the study period.
- **Pre-planned or elective hospitalization:** A hospitalization planned before signing the informed consent form is not considered an SAE, but rather a therapeutic intervention. However, if during the pre-planned hospitalization an event occurs, which prolongs the hospitalization or meets any other SAE criteria, the event will be considered an SAE. Surgeries or interventions that were under consideration, but not performed before enrollment in the study, will not be considered serious if they are performed after enrollment in the study for a condition that has not changed from its baseline level. Elective hospitalizations for social reasons, solely for the administration of chemotherapy, or due to long travel distances are also not SAEs.

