11.4. Documenting and Reporting of Adverse Events and Serious Adverse Events by Investigators

11.4.1. Assessment of Adverse Events

Investigators will assess the occurrence of adverse events and serious adverse events at all subject evaluation timepoints during the study. All adverse events and serious adverse events whether volunteered by the subject, discovered by study personnel during questioning, detected through physical examination, all abnormal laboratory values, or other means, will be recorded. Each recorded adverse event or serious adverse event will be described by its duration (ie, start and end dates), severity, regulatory seriousness criteria (if applicable), suspected relationship to the investigational product, and any actions taken.

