11.4.2. Adverse Event Reporting Period

All AEs whether serious or non-serious, will be captured from the time signed and dated ICF is obtained until 30 days following the last dose of study drug.

Serious adverse events reported after 30 days following the last dose of study drug should also be reported if considered related to study drug. Resolution information after 30 days should be provided.

Progressive disease should NOT be reported as an event term, but instead symptoms/clinical signs of disease progression may be reported. (See Section 11.1.1)

All adverse events, regardless of seriousness, severity, or presumed relationship to study drug, must be recorded using medical terminology in the source document. All records will need to capture the details of the duration and the severity of each episode, the action taken with respect to the study drug, investigator's evaluation of its relationship to the study drug, and the event outcome. Whenever possible, diagnoses should be given when signs and symptoms are due to a common etiology (eg, cough, runny nose, sneezing, sore throat, and head congestion should be reported as "upper respiratory infection").

All deaths should be reported with the primary cause of death as the AE term, as death is typically the outcome of the event, not the event itself.

If a death occurs within 30 days after the last dose of study drug, the death must be reported as a serious adverse event.

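### Section 10.5 counts adverse events rather than patients, so the planned safety table does not identify the proportion of patients with a toxicity

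*Combined protocol and SAP*

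**What the plan says.** The secondary-endpoint paragraph of Section 10.5 sets out the adverse-event summary: "Number and type of adverse events will be summarized descriptively by system organ class affected and by grade of event", overall and split by dose. It names no percentage, denominator or rule for a patient who has the same event twice or at two grades.

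The same paragraph treats RECIST response differently. Response "will be summarized by the number and percentage of patients, accompanied by 2-sided exact 95% confidence intervals".

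A denominator is available. Section 10.4.1 states: "The safety population will include all patients who receive at least one dose of either study drug". Section 10.5 does not link the adverse-event summary to it.

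Nothing else in Section 10.5 supplies a patient-level toxicity rate. Laboratory results and vital signs get a mean, SD and range, which does not show how many patients reached a given grade. Dose-limiting toxicity is defined in Section 5.2.1, but Section 10.5 has no summary of it. Relatedness is assessed (Section 11.1.4) and recorded (Section 11.4.1), but Section 10.5 does not use it.

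On recording, Section 11.4.2 says: "All records will need to capture the details of the duration and the severity of each episode".

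**The concern.** Sections 2.2 and 10.2.2 make safety of the combination a secondary objective. In a small Phase Ib/II combination study, readers will ask what share of patients had a given toxicity, and what share had a related one of Grade 3 or worse. A table of event counts answers neither.

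There are three consequences:

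- A count above one in a cell may come from one patient or from several, and the table does not say which.
- A patient with a Grade 1 and later a Grade 3 episode of the same event appears in two cells, so cells cannot be added up to patients.
- An exact binomial interval cannot be put on an event count. Events within a patient are not independent trials, and the number of trials is undefined.

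**Working it through.** **1. The plan's own figure.** The documents state no figure for the adverse-event table. Their only design figure is the efficacy rule in Section 10.3: 15 or more of 25, 40% against 70%, one-sided level 0.034, power 90%. With X binomial(25, p), P(X ≥ 15) is 0.0344 at p = 0.40 and 0.9022 at p = 0.70. Both stated values reproduce. This point does not depend on them.

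**2. The two summaries in the same paragraph of Section 10.5.**

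| | RECIST response | Adverse events |
|---|---|---|
| Unit | patient | event |
| Percentage | yes | none stated |
| Denominator | patients | none stated |
| Interval | exact 95%, two-sided | none stated |
| Rule for repeats | not needed | none stated |

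**3. What an event count says about patients.** If a cell holds E ≥ 1 events among N treated patients, the number affected, k, can be any whole number from 1 to min(E, N). The risk k/N is fixed only when E is 0 or 1.

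Assumptions for illustration: E = 12, which is hypothetical, and N = 30, the accrual target in Section 10.3. The exact 95% limits are the 0.025 quantile of Beta(k, N − k + 1) and the 0.975 quantile of Beta(k + 1, N − k).

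| Patients behind the 12 events | k/30 | Exact 95% CI |
|---|---|---|
| 1 | 3.3% | 0.1% to 17.2% |
| 3 | 10.0% | 2.1% to 26.5% |
| 6 | 20.0% | 7.7% to 38.6% |
| 12 | 40.0% | 22.7% to 59.4% |

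The intervals for 1 and 12 patients do not overlap, yet the planned table would look the same. With N = 25 the range is 1/25 = 4.0% (0.1% to 20.4%) to 12/25 = 48.0% (27.8% to 68.7%), so the result does not depend on the exact number treated.

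**4. By dose.** Section 5.2.1 gives two dose levels and fixes no number of patients for either. If the levels treat n₁ and n₂ patients, equal event counts mean events per patient in the ratio n₂ : n₁. Raw counts are therefore not comparable unless the sizes are equal, and Section 10.5 does not call for the sizes to be shown with the counts.

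**5. Against the protocol's reference rates.** The nivolumab rates it quotes are per patient: pneumonitis 6/268 = 2.2% (Section 5.3.4.6), hypothyroidism 21/268 = 7.8%, given as 8% (Section 5.3.4.5), and immune-mediated nephritis or renal dysfunction 2/268 = 0.7% (Section 5.3.4.4). An event count has no matching numerator.

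**6. What patient counting would give.** Per-patient rates are informative even at this size. With 0 of 30 affected, the exact two-sided 95% upper limit is 1 − 0.025^(1/30) = 0.116, or 11.6%.

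**The case against.** The strongest reply is that the sentence in Section 10.5 is a brief description, not an exclusive table specification. Events are recorded per subject with dates, severity and relatedness (Section 11.4.1), the adverse-event form follows each cycle (Section 12.7), and Section 10.4.1 defines the safety population in patients. A statistician could derive patient-level incidence without new data. All of that stands: no information is lost. But the plan does not commit to those tables, and the authors used patient wording for response in the same paragraph.

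It is also fair that this is a secondary, descriptive endpoint. The primary endpoint and its decision rule are untouched.

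A reader might go further and infer that repeat events, especially fluctuating laboratory values, will dominate the counts. The documents do not support that:

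- **Section 11.4.1.** The phrase "all abnormal laboratory values, or other means, will be recorded" belongs to a sentence whose subject is adverse events. It can be read as naming laboratory values as one way an event is detected.
- **Section 11.1.1.** It describes an adverse event as "including a clinically significant abnormal laboratory finding, for example", but only as an example, and its bullet list later names laboratory abnormalities without that qualifier. It supplies no clear limit to carry into Section 11.4.1.
- **Section 11.4.2.** The sentence on episodes governs source records, not table counts. The same paragraph asks for signs and symptoms of common cause to be reported as one diagnosis where possible.
- **Number of draws.** The schedule allows about 20 hematology draws per patient (14 in cycles 1 to 7, 6 in cycles 8 to 13), but only over a full year on treatment. Section 1.1.1 quotes median progression-free survival of 2.7 to 4.2 months for nivolumab alone, so 20 is better read as a ceiling than as typical.

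Repeat events can distort the table. How often they would is unknown, and the documents hold no data on it.

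**Conclusion.** The point holds as a defect in the planned summary, not in data capture. Followed as written, Section 10.5 gives event totals that do not determine the proportion of patients affected. In the illustration the possible risk spans 40.0 − 3.3 = 36.7 percentage points. That span rests on a hypothetical cell of 12 events and 30 treated patients. The counting-unit problem itself rests only on the wording of Section 10.5 and on finding no patient-level toxicity incidence planned elsewhere, so it stands under any reading of the laboratory and episode wording.

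If no patient had a repeat event, event and patient counts would agree, but the planned table would not let a reader know that. The change is worth making before the analysis, so that the counting rule is not chosen after the data are seen.

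**What to change.** Replace the adverse-event sentence in Section 10.5 with wording to this effect:

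*For the safety population, report the number and percentage of patients with at least one adverse event, by system organ class, term and grade. Count each patient once, at worst grade, within each term and each organ class. Present results overall and by assigned dose level, with the number of treated patients at each level. For treatment-related events of Grade 3 or worse, add exact two-sided 95% confidence intervals. Event counts may be shown as a supplement.*

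The new text should say which Section 11.1.4 categories count as treatment-related; possibly related and related would be consistent with Section 5.2.1, which counts a possible relation for dose-limiting toxicity.

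No change to Section 11.4.1 or to laboratory recording is needed, because counting each patient once at worst grade already removes the effect of repeats.

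Cost: one passage of text and standard programming, with no added data, visits or patients. Because Section 10.5 is part of the protocol, the edit follows the amendment route in Section 12.9 (review and approval by the company supplying ibrutinib, then IRB approval) and can go in with any other amendment.
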